1 ABBREVIATIONS

Abbreviation	Description
AZM	Azithromycin
DSMB	Data Safety Monitoring Board
HCQ	Hydroxychloroquine
SOC	Standard of Care

2 INTRODUCTION

The purpose of this document is to describe statistical analysis plans for the PROTECT Trial interim and final analyses. It includes an overview of the project, description of endpoints, general analysis conventions, analysis populations, handling of missing data, statistical analyses, and guidelines for interpreting interim analysis results. The statistical team intends to perform all statistical analyses as specified in the protocol. However, it is conceivable that unanticipated changes to the course of the study may preclude some scheduled analyses. Study conditions or analysis results may identify a need for additional data review.

3 STUDY DESIGN AND OBJECTIVES

PROTECT is an open-label, factorial randomized clinical trial with two factors and nested randomization. Patients hospitalized with confirmed SARS-CoV-2 infection will be initially randomized to one of two arms in a 1:1 ratio: 1) Standard of care treatment or 2) Standard of care treatment plus 5 days of hydroxychloroquine (HCQ). Patients with no contraindication to azithromycin (AZM) who have not received AZM in the seven days prior to enrollment will undergo a second randomization in a 1:1 ratio to either receive 1) No AZM or 2) 5 days of AZM. The resulting treatment group combinations are summarized in Table 1. Participants will be followed for 28 days after randomization or until hospital discharge, whichever is later. The primary endpoint is the World Health Organization (WHO) ordinal scale for clinical improvement as measured on day 14 after randomization (see Section 6.1 for details).

Table 1. Treatment groups

	AZM: No	AZM: Yes	AZM: Not Eligible
HCQ: No	Group 1: SOC	Group 3: SOC + AZM	Group 5: SOC, AZM-ineligible
HCQ: Yes	Group 2: SOC + HCQ	Group 4: SOC + HCQ + AZM	Group 6: SOC + HCQ, AZM-ineligible

HCQ = hydroxychloroquine, AZM = azithromycin, SOC = standard of care

Hypothesis #1 (HCQ versus no HCQ): Groups 2+4+6 versus 1+3+5

Hypothesis #2 (AZM versus no AZM): Groups 3+4 versus 1+2

3.1 Primary Objective

The PROTECT trial aims to simultaneously test the following two primary hypotheses:

- **Hypothesis #1 (HCQ versus no HCQ):** The addition of HCQ improves outcomes as measured by the day 14 WHO ordinal scale (primary endpoint) when added to standard of care and possible concomitant AZM. The analysis will be a comparison of groups 2+4+6 versus 1+3+5 as defined in Table 1.
- **Hypothesis #2 (AZM versus no AZM):** The addition of AZM improves outcomes as measured by the day 14 WHO ordinal scale (primary endpoint) when added to standard of care and possible concomitant HCQ. The analysis will be a comparison of groups 3+4 versus 1+2 as defined in Table 1.

3.2 Secondary Objectives

The trial will also evaluate the HCQ and AZM hypotheses using the following secondary endpoints:

- Mortality during the index hospitalization
- Number of days on mechanical ventilation during the index hospitalization
- Progression to mechanical ventilation during index hospitalization
- World Health Organization ordinal scale on day 28
- Days from randomization until hospital discharge
- Duration of fever after randomization
- Duration of supplemental oxygen use after randomization

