6 DESCRIPTION OF EFFICACY ENDPOINTS

6.1 Primary Endpoint

The primary outcome measure is the World Health Organization (WHO) ordinal scale for clinical improvement as measured on day 14 after randomization. The WHO scale has 9 levels numbered 0 to 8 with 0 denoting no clinical or virologic evidence of infection and 8 denoting death.

Table 2. World Health Organization ordinal scale for clinical improvement

Descriptor	Score
No clinical or virologic evidence of infection	0
No limitation of activities	1
Limitation of activities	2
Hospitalized, no oxygen therapy	3
Oxygen by mask or nasal cannula	4
Non-invasive ventilation or high-flow oxygen	5
Intubation and mechanical ventilation	6
Mechanical ventilation + additional organ support (pressors, renal replacement therapy, ECMO)	7
Death	8

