7.1 Missing Data

Every effort will be made to obtain complete data. In the case where missing data remain, the following procedures will be followed. These procedures are based on the assumption that missing data will be rare and may be revised if that assumption is violated.

- **Primary endpoint.** If a day 14 WHO scale assessment is unavailable then analysis will be based on the closest assessment within 21 days of randomization with ties broken by taking the earlier assessment. If a patient is known to have died or been re-hospitalized but the exact date is unknown then data entry may be based on an estimated value. If no estimate of a patient's status is available within 21 days of randomization then the primary endpoint will be regarded as missing and will not be imputed. The approach to handling missing primary endpoint data may be revised if >5% of patients have no assessments within a window of 14 ± 3 days or >2% of patients have no assessments within a window of 14 ± 6 days.
- **Mortality during the index hospitalization.** Missing in-hospital mortality status will not be imputed.
- **Number of days on mechanical ventilation during index hospitalization.** No imputation will be performed for this endpoint.
- **Progression to mechanical ventilation during index hospitalization.** No imputation will be performed for this endpoint.
- **Day 28 WHO scale.** If unavailable then analysis will use the closest measurement from days 14 to 40 with ties broken by taking the later assessment. Data entry may be based on estimated dates if exact dates for a status assessment is unavailable.
- **Days from randomization until hospital discharge.** No imputation will be performed for this endpoint.
- **Duration of fever after randomization.** No imputation will be performed for this endpoint.
- **Duration of supplemental oxygen use after randomization.** No imputation will be performed for this endpoint.

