9 ANALYSIS OF SECONDARY EFFICACY ENDPOINTS

The major treatment group comparisons of HCQ versus no HCQ and AZM versus no AZM will be repeated using the following secondary clinical endpoints in place of the primary endpoint:

- Mortality during the index hospitalization
- Number of days on mechanical ventilation during the index hospitalization
- Progression to mechanical ventilation during index hospitalization.
- Day 28 WHO ordinal scale
- Days from randomization until hospital discharge
- Duration of fever after randomization
- Duration of supplemental oxygen use after randomization

Analysis of **index hospitalization mortality status** and **mechanical ventilation** will be performed using logistic regression. The analysis will use the same predictors as the primary endpoint proportional odds model and will use the same Bayesian prior distribution for the main effects and interaction effects parameters. For the ventilation endpoint, patients on ventilator at baseline will be excluded. To facilitate interpretation, parameter estimates from the logistic regression model will be re-expressed as win ratios, risk ratios, and/or risk differences.

Analysis of the **day 28 WHO scale** will be identical to the primary endpoint analysis using the day 28 assessment in place of the 14 day assessment.

Analysis of **length of hospital stay, duration of fever, and duration of supplemental oxygen use** will be based on a continuation ratio model for discrete time-to-event data treating death as a competing risk. For length of stay, the continuation ratio approach models that probability of being discharged on day $d + 1$ conditional on being alive and in-hospital on day d and assumes that covariates have a multiplicative effect on this probability. For patients who die prior to discharge, the patient's discharge date will be set to the last date of the patient's potential follow-up time. The interpretation is similar for duration of fever and supplemental oxygen. Predictor variables in the continuation ratio model will be identical to the primary endpoint proportional odds model and will use a similar prior distribution for the main effects and interaction terms.

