10 PRESENTATION OF SAFETY DATA

Safety data will be collected for all randomized participants from the time of randomization through day 28 unless the participant withdraws from the study before day 28. The information to be collected on safety-related events includes event narratives, investigator-assigned likelihood of relatedness to study treatments (unlikely, possibly, probably), distinctions between serious and non-serious adverse events, expectedness of the event, and the event outcome. Event severity will be classified using the Common Terminology Criteria for Adverse Events (CTCAE) v3.0. Tabulations of these data will be performed in the intention to treat population using the treatment groups defined in Section 5.1. Safety data will be tabulated by treatment group and will include the following.

- Frequency and percentage of serious adverse events (SAEs) overall, by treatment group, and by various cross classifications of treatment group, CTCAE classification, expectedness, relatedness to study treatments, and outcome.
- Frequency and percentage of all-cause study drug discontinuation overall and by treatment group
- Frequency and percentage of each of the following adverse events of special interest (EOSI) overall and by treatment group:
 - Arrhythmias (ventricular), not including torsade de pointes
 - Torsade de pointes
 - Hepatic Failure
 - Bone marrow failure
 - Aplastic anemia
 - Prolonged QT interval
 - Angioedema
 - Exfoliative dermatitis
 - Acute generalized exanthematous pustulosis (AGEP)

- Psychosis
- Suicidal Ideation
- Seizure
- Narrative descriptions of unanticipated problems
- Patient- and event-level listings and additional tabulations as requested by the DSMB

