Table 5. Proposed guidelines for DSMB statistical monitoring

	Definition	Monitoring Guideline
Moderate efficacy.	Win Ratio ≥ 1.25 favoring study drug over no study drug	Signal if probability is $>80\%$
Any efficacy	Win Ratio >1.0 favoring study drug over no study drug	Signal if probability is $>95\%$

Inefficacy	Win Ratio <1.0 favoring no study drug over study drug	Signal if probability is >80%
Moderate harm	Win Ratio <0.9 favoring no study drug over study drug	Signal if probability is >75%

Note: Study drug refers to the comparison of HCQ versus no HCQ (hypothesis #1) or the comparison of AZM versus no AZM (hypothesis #2). Win ratios will be estimated for both the primary endpoint and death during the index hospitalization.

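### The only stand-alone death endpoint, which is also monitored under Table 5, closes at hospital discharge, so deaths after discharge are non-events and harm in that period can be missed

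*SAP*

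**What the plan says.** SAP 3.2 lists "Mortality during the index hospitalization" as a secondary endpoint. Sections 7.1, 9 and 11 use the same definition, and no other stand-alone mortality endpoint is defined. Section 9 states that its analysis "will be performed using logistic regression", with no time horizon and no rule for patients discharged alive.

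Section 11 makes this endpoint one of the two interim efficacy endpoints, beside the day 14 WHO scale. The note to Table 5 reads "Win ratios will be estimated for both the primary endpoint and death during the index hospitalization", so all four guidelines apply to it.

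Observation continues after discharge. Section 3 says "Participants will be followed for 28 days after randomization or until hospital discharge, whichever is later". The WHO scale in 6.1 runs from "0 denoting no clinical or virologic evidence of infection and 8 denoting death", without limiting death to hospital. It is also analysed at day 28, and for a missing day 28 value 7.1 says "If unavailable then analysis will use the closest measurement from days 14 to 40 with ties broken by taking the later assessment". Section 10 says "Safety data will be collected for all randomized participants from the time of randomization through day 28", unless the participant withdraws.

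**The concern.** The window for counting a death ends at an event that follows randomization. Each drug is tested for an effect on that event, since days to discharge is another endpoint in 3.2, and the trial is open-label. The window also has a different length for each patient: a death on the ward on day 50 counts, while a death at home on day 16, or on readmission on day 20, does not.

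Two things follow. If the share of deaths after discharge differs between arms, the death win ratio reflects discharge timing as well as survival. And an excess of deaths after discharge on one arm leaves the death comparison seen by the DSMB unchanged, whatever its size.

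**Working it through.** The SAP gives no mortality rate, power or sample size for death, so there is no figure of its own to reproduce. The check has two parts.

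**1. Where a death after discharge is counted.**

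| Analysis | Death after discharge by day 14 | Death after discharge, days 15–28 | Under Table 5? |
|---|---|---|---|
| Index-hospitalization mortality | non-event | non-event | yes |
| Day 14 WHO scale | scores 8 | normally not counted | yes |
| Day 28 WHO scale | scores 8 | scores 8 | no |
| Safety tables | may appear | may appear | no |

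The non-event entries are implied rather than written: a patient discharged alive did not die in hospital, and the SAP gives no other handling. The word normally is needed because 7.1 lets a missing day 14 value be replaced by the closest assessment within 21 days.

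**2. Illustration of size.** Inputs from the SAP are the main-effect prior SD of 0.3537 on the log odds ratio (8.4) and 500 monitored patients (11.1), taken as 250 per arm. Mortality rates and post-discharge shares are assumptions.

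In-hospital risk = 28-day risk × (1 − share of deaths after discharge). For a binary outcome, with pT and pC the risks on drug and control, win ratio = (1 − pT)pC / [pT(1 − pC)], the odds ratio for survival.

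(a) No true effect: 12% 28-day mortality in both arms and a control share of 5%, so pC = 0.12 × 0.95 = 0.114.
- Share on drug 5%: pT = 0.114, win ratio 1.00.
- Share on drug 10%: pT = 0.108, win ratio (0.892 × 0.114)/(0.108 × 0.886) = 1.06.
- Share on drug 15%: pT = 0.102, win ratio (0.898 × 0.114)/(0.102 × 0.886) = 1.13.
- Share on drug 20%: pT = 0.096, win ratio (0.904 × 0.114)/(0.096 × 0.886) = 1.21.

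Table 5 acts on posterior probabilities, so these win ratios must be converted. With v = 1/[250 pT(1 − pT)] + 1/[250 pC(1 − pC)], a normal approximation gives posterior mean log(win ratio) × 0.3537²/(0.3537² + v) and variance 1/(1/0.3537² + 1/v). For the 20% case, v = 0.0857, the mean is 0.192 × 0.5935 = 0.114 and the SD is 0.2255. P(win ratio > 1) is then 0.69, against a guideline of more than 95%, and P(win ratio ≥ 1.25) is 0.31, against more than 80%. With 28-day mortality of 10%, 15% and 20% and the same shares, the win ratio is 1.21, 1.22 and 1.23, and P(win ratio > 1) is 0.67, 0.72 and 0.77.

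(b) Harm only after discharge: in-hospital mortality 10% in both arms, with all excess deaths on drug occurring after discharge and none on control.

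| Excess on drug | Day 28 win ratio | P(<1.0), guideline >80% | P(<0.9), guideline >75% |
|---|---|---|---|
| +2 points | 0.81 | 0.71 | 0.53 |
| +4 points | 0.68 | 0.86 | 0.72 |
| +6 points | 0.58 | 0.94 | 0.86 |

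For in-hospital death the win ratio is 1.00 in every row, with P(<1.0) = 0.50 and P(<0.9) = 0.32. Death by day 28 would thus raise the inefficacy signal at +4 points and both signals at +6. In-hospital death raises neither.

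**The case against.** The strongest defence is that the endpoint is worded consistently throughout, that in-hospital mortality is a recognised choice which may have been made in the protocol, and that deaths after discharge are not lost to the trial. They score 8 on the day 14 scale if they occur by then and on the day 28 scale, which is analysed in the same way as the primary endpoint. The DSMB also receives safety tables. All of this stands. It narrows the gap to the mortality model and the Table 5 death comparison but does not close it.

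A reader might infer that the definition would produce a false efficacy signal. The documents do not support that: Table 5 acts on posterior probabilities, and the assumed scenarios fall well short of its efficacy guidelines. Nor does earlier discharge alone create bias; the share of deaths after discharge must differ by arm. A reader might also see a contradiction in two tables with different death counts, but an in-hospital count and a day 28 count may properly differ.

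A further inference would be that day 28 vital status is assured for everyone. The sentence in 7.1 that opens "If a patient is known to have died or been re-hospitalized but the exact date is unknown then data entry may be based on an" belongs to the day 14 endpoint, and a missing day 28 scale value may come from as early as day 14. Follow-up to day 28 is planned, but its completeness is not guaranteed.

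Finally, replacing the endpoint outright would discard in-hospital deaths after day 28 and leave many outcomes open at the first review, which is triggered by day 14 data on 75 participants. Both points are valid and shape the remedy.

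**Conclusion.** The concern holds as a weakness of the endpoint definition, worth correcting because the follow-up needed is already planned. The death window depends on discharge timing, and a death after discharge on days 15 to 28 normally falls outside both endpoints monitored under Table 5.

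The size is unknown, because the SAP gives neither mortality nor the share of deaths after discharge. Under the assumed 12% mortality the null win ratio shifts to between 1.06 and 1.21 for shares of 10% to 20% against 5%, and not at all if the shares are equal. The missed-harm result is the more important one, but it rests on the extreme assumption that all excess deaths come after discharge. Even then, an excess of 2 points would raise no Table 5 signal under either definition. The posterior probabilities are normal approximations for a single main effect, with observed data equal to expectation.

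**What to change.** In 3.2, 7.1, 9, 11 and the Table 5 note, make all-cause death within 28 days of randomization, wherever it occurs, the main mortality analysis. Keep index-hospitalization mortality, including in-hospital deaths after day 28, as a supportive analysis.

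At interim looks, count every death known to have occurred within 28 days of randomization regardless of location, report it beside in-hospital death, and state how many patients have not yet reached day 28.

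This means redefining one endpoint in the SAP, aligning the protocol if it uses the same definition, and deriving one variable from follow-up already planned. Some discharged patients will have unknown vital status at day 28, which should be counted and reported by arm, and day 28 data will be incomplete at early looks.

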3.3 Tertiary Objectives (Exploratory)

The trial will perform additional exploratory pairwise treatment group comparisons for the primary and secondary endpoints as follows (see Table 1 for definitions of study groups):

- SOC + HCQ versus SOC (group 2 versus 1)
- SOC + AZM versus SOC (group 3 versus 1)
- SOC + HCQ + AZM versus SOC (group 4 versus 1)
- SOC + AZM versus SOC + HCQ (group 3 versus 2)
- SOC + HCQ + AZM versus SOC + HCQ (group 4 versus 2)
- SOC + HCQ + AZM versus SOC + AZM (group 4 versus 3)

4 RANDOMIZATION METHODOLOGY

Patients meeting entry criteria will be stratified by eligibility to undergo randomizations for both study drugs or only HCQ.

Stratum 1: Eligible for both study drugs

Participants who are eligible for both study drugs will be randomized in a 1:1:1:1 ratio to one of the following:

Group	Description
-------	-------------

1	Standard of Care
2	Standard of Care + HCQ
3	Standard of Care + AZM
4	Standard of Care + HCQ + AZM

Stratum 2: Ineligible for azithromycin

Participants who are ineligible to be randomized to azithromycin will be randomized in a 1:1 ratio to one of the following groups

Group	Description
5	Standard of Care --
6	Standard of Care + HCQ

Randomizations within each stratum will use permuted blocks with random block sizes and will be further stratified by ventilator status at baseline.

5 POPULATIONS FOR EFFICACY AND SAFETY ANALYSES

5.1 Intention-to-treat population

The intention-to-treat (ITT) population will include all participants who receive a randomized treatment assignment, including those who are later determined not to meet trial eligibility criteria, unless the randomization was an unintentional administrative error, as determined by the coordinating center at the Duke Office of Clinical Research. Patients will be assigned to treatment groups based on each patient's randomized treatment group assignment regardless of which treatment if any the patient actually received.

6 DESCRIPTION OF EFFICACY ENDPOINTS

6.1 Primary Endpoint

The primary outcome measure is the World Health Organization (WHO) ordinal scale for clinical improvement as measured on day 14 after randomization. The WHO scale has 9 levels numbered 0 to 8 with 0 denoting no clinical or virologic evidence of infection and 8 denoting death.

Table 2. World Health Organization ordinal scale for clinical improvement

Descriptor	Score
No clinical or virologic evidence of infection	0
No limitation of activities	1
Limitation of activities	2
Hospitalized, no oxygen therapy	3
Oxygen by mask or nasal cannula	4
Non-invasive ventilation or high-flow oxygen	5
Intubation and mechanical ventilation	6
Mechanical ventilation + additional organ support (pressors, renal replacement therapy, ECMO)	7
Death	8

7 GENERAL ANALYSIS CONSIDERATIONS

Analyses will be performed according to the principle of "intention-to-treat" with subjects analyzed (and endpoints attributed) according to the group to which enrolled subjects were randomized, regardless of subsequent medications or treatment crossover. All major treatment group comparisons will be performed using Bayesian statistical methods. The output of a Bayesian analysis is a posterior probability distribution describing the relative likelihood of different numerical estimates for unknown quantities. This posterior distribution can be used to determine the likelihood of a clinically important treatment benefit or harm in light of the study data. The Bayesian approach provides an especially useful perspective for interpreting results of small studies that are likely to be accompanied by substantial statistical uncertainty. The Bayesian analog of a confidence interval, known as a credible interval, has a direct and intuitively appealing interpretation as an interval containing the true value with a specified probability. Point estimates will be calculated as posterior means and accompanied with 95% equal-tailed credible intervals. Analysis results will also be framed in terms of probability statements, for example, the probability that the study drugs lead to improved outcomes on the primary endpoint. The analysis plan does not include frequentist hypothesis testing and does not make adjustment for multiple comparisons. Additional considerations related to multiple comparisons are discussed in Sections 11.1.

7.1 Missing Data

Every effort will be made to obtain complete data. In the case where missing data remain, the following procedures will be followed. These procedures are based on the assumption that missing data will be rare and may be revised if that assumption is violated.

- **Primary endpoint.** If a day 14 WHO scale assessment is unavailable then analysis will be based on the closest assessment within 21 days of randomization with ties broken by taking the earlier assessment. If a patient is known to have died or been re-hospitalized but the exact date is unknown then data entry may be based on an estimated value. If no estimate of a patient's status is available within 21 days of randomization then the primary endpoint will be regarded as missing and will not be imputed. The approach to handling missing primary endpoint data may be revised if >5% of patients have no assessments within a window of 14 ± 3 days or >2% of patients have no assessments within a window of 14 ± 6 days.
- **Mortality during the index hospitalization.** Missing in-hospital mortality status will not be imputed.
- **Number of days on mechanical ventilation during index hospitalization.** No imputation will be performed for this endpoint.
- **Progression to mechanical ventilation during index hospitalization.** No imputation will be performed for this endpoint.
- **Day 28 WHO scale.** If unavailable then analysis will use the closest measurement from days 14 to 40 with ties broken by taking the later assessment. Data entry may be based on estimated dates if exact dates for a status assessment is unavailable.
- **Days from randomization until hospital discharge.** No imputation will be performed for this endpoint.
- **Duration of fever after randomization.** No imputation will be performed for this endpoint.
- **Duration of supplemental oxygen use after randomization.** No imputation will be performed for this endpoint.

